9. DATA MANAGEMENT AND PROCEDURE TO GUARANTEE PATIENT DATA CONFIDENTIALITY

The individual pain centers, which are the sources of the data, are responsible for detecting, enrolling, coding and recording cases and are functionally linked to the primary center from which they draw methodological indications of an operational nature. Sensitive data will be noted, anonymized through an encryption procedure, and stored in a secure place.

10. SECURITY AND ADVERSE EVENTS

This observational study will be conducted according to the current protocol. This is a non-interventional observational study. Any study based on this registry will not receive any guidance on the treatment of patients. Complications and adverse events that occur during follow-ups will be recorded in the registry.

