- continuously and systematically collect, evaluate, and archive relevant demographic and clinical information on patients belonging to chronic pain treatment centers, making it available for studies and research.
- promote the use of uniform and comparable classification systems, definitions, and records in the structures participating in the database.

- Define the flow of patients referring to pain therapy centers to allow adequate health planning and the priority areas of intervention of the national health plan.

The data collected will facilitate the planning of future studies aimed to:

- define the impact of chronic pain at a local and national level, and its territorial and temporal variations over time, through prevalence and incidence measures;
- identify clinical subtypes, risk factors, predisposing and triggering factors;
- increase knowledge in the field of chronic pain to standardize diagnostic/therapeutic pathways and promote adequate management strategies.

2. Objectives

Primary Outcomes

Identify the profiles of patients belonging to pain therapy centers in terms of:

1. Location and type of pain
2. Prescribed therapies
3. Effectiveness of therapies
4. Time needed to reach the efficacy outcome

Secondary Outcome

1. Evaluate the proportion of patients who reach the outcome of 30 or 50% improvement
2. Evaluate the healthcare resources used in terms of number of visits and time needed to achieve the best outcome (30 or 50% improvement)
3. Identify patient profiles that are related to clinically significant outcomes and the specific treatments performed, plus their intermediate surrogate outcomes in relation to specific patterns

4. Describe the relevant clinical variables in the study population. In particular, the absolute and relative frequencies of those clinical variables relevant to the effectiveness of the treatment will be described, categorized by type of treatment, and the timing of the start of treatment with respect to the onset of pain. The data collected may be used for predictive analyses.

3. Study Design

This is a prospective, multicenter, non-profit observational cohort study. No intervention on patients outside of common clinical practice is envisaged.

The study is divided into three phases.

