5. PROCEDURES EXPECTED AND INFORMATION COLLECTED

Enrollment procedure

Adult patients of both sexes who belong to pain therapy centers with a diagnosis of Chronic Pain (pain that lasts > 12 weeks), regardless of the etiology, modality and age of onset, will be considered eligible for enrollment.

It will be possible to enroll patients during their first visit (FIRST ANESTHESIOLOGICAL VISIT), or during a check-up visit (ANESTHESIOLOGICAL CHECK-UP VISIT) or during a scheduled hospitalization for pain procedures (ORDINARY OR DAY HOSPITAL ADMISSION)

Patients will be asked to join the study after having been informed in detail (also with the aid of a written information form) of the objectives of the project, as well as the methods with which these objectives will be pursued. Participants will be informed about the lack of informative feedback regarding the results of future clinical evaluations: the results of any research originating from the register, in fact, will not be delivered to the participants themselves. The subject who freely accepts will authorize the inclusion of their data in the project by signing the informed consent form of which they will receive a copy. It will also be clearly explained in the information sheet attached to the informed consent that each participant will have the possibility of withdrawing their participation from the study at any time, without providing any reason and without this jeopardizing the doctor-patient relationship with the specialists involved in the project.

Patients will be informed by the manager of the patient's pain center or the principal investigator for the center (assuming this is not the same individual).

The doctor will complete the electronic CRF after evaluating the patient and classifying him according to the criteria of the IASP (International Association for the Study of Pain) in terms of primary or secondary chronic pain. In the case of a patient enrolled during a check-up or during hospitalization, all data relating to the time in which the patient is in care at the center, the

invasive procedures previously undertaken, the drugs prescribed, will be collected. Retrospective data (only for patients already being treated at the center) will be collected according to a predefined group (e.g.: the patient has been in the care of the center for: > 5 years; from 1 to 5 years; from 1 year to 6 months; from 3 to 6 months; < 3 months).

[figure not shown]
Follow-up procedure

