Once enrolled, the patient will be followed prospectively until the end of enrollment. At each visit it will be possible to retrieve the patient's chart and fill in the data relating to the intensity of pain and the treatments undertaken. It will also be possible to modify or add an etiological diagnosis in forms of secondary chronic pain. There is no limit to the number of follow-ups for each patient as long as the database is active (3 months from the date of enrollment of the last patient, considering a 12-month active enrollment expected for this study).

Data gathered

The activities of the registry do not replace routine diagnostic tests or visits to your doctor. The data collected by the registry will include relevant demographic data of the patient, comorbidities, the duration of the pain (> 5 years; from 1 to 5 years; from 1 year to 6 months; from 3 to 6 months), the type of pain, the location of the pain, the intensity of the pain (Brief Pain Inventory- Severity (BPI-S) and pain interference in daily activities (Brief Pain Inventory- Interference (BPI-I), treatments received (categorized according to pharmacological therapy, infiltrative therapy, ablative or neuromodulatory therapy, implants), the tests conducted, the number of other medical specialists contacted for the pathology being studied, the professional who sent it to the center. Specifically, the data collected is shown in Attachment 1
In particular, patients will be characterized by:

Type of pain (chronic primary or chronic secondary according to the scheme proposed by IASP)

Location of pain according to the following scheme (multiple options are possible)

- Lower back pain
- Thoracic
- Upper arts
- Lower limbs
- Head/Neck
- Pelvis

Pain Intensity

Brief Pain Inventory-Severity (BPI-S)

Interference with daily activities

Brief Pain Inventory-Interference (BPI-I)

Clinical information related to the pathology

Therapy
Pharmacological
Infiltrative
Implantable

Data collection methods and anonymization

The data collected will be used for scientific and epidemiological purposes. Each data will be created by a participating center and recorded on the SIAARTI Servers via a web application using the RedCap® data management software.

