6. ENDPOINT

Primary Endpoint

The number of patients referring to the centers, the type of pain, the proportion of patients who reach the clinically significant outcome, the type of therapies prescribed (pharmacological, neuromodulatory or implanted) necessary to achieve the outcome and the number of accesses and the Time in which a clinically significant improvement will be achieved (Change in BPI-s or BPI-I; a reduction of > 30% is considered clinically significant and a reduction of > 50% is considered optimal, the data will be evaluated for each Item).

Secondary Endpoint

1. The effectiveness of the treatments will be described in terms of
 - a. Change in pain intensity according to the Brief Pain Inventory-Severity questionnaire (BPI-S) A reduction of > 30% is considered clinically significant and optimal a reduction > of 50% the data will be evaluated for each Item)
 - b. b. Change in pain interference on daily activities according to the Brief Pain Inventory-Interference questionnaire (BPI-I). A reduction of > 30% is considered clinically significant and a reduction of > 50% is considered optimal; the data will be evaluated for each item)
2. Proportion of patients achieving clinically significant outcomes in relation to baseline characteristics and specific treatments performed and their intermediate surrogate outcomes in relation to specific patterns.
3. Resources used: Number of visits to the center for each patient in a year; Number of ordinary or day hospitalizations for each patient in a year.
4. The clinical variables relevant to the outcome will be described (e.g. type of pain, comorbidities, the time between treatment and clinically significant improvement, type of therapy undertaken - pharmacological, invasive, implant-based)

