12. ETHICAL CONSIDERATIONS

This observational study is designed and will be conducted according to the current protocol, in accordance with EU Directive 2001/20/EC relating to the implementation of the principles of good clinical practice in the conduct of clinical trials on medicinal products for human use, in accordance with the principles published in Good Clinical Practice (GCP) guidelines and in accordance with the Declaration of Helsinki on Ethical Principles for Medical Research Involving Human Subjects, adopted by the General Assembly of the World Medical Association (1996),

The investigator guarantees that personal patient data will be protected and processed in accordance with the General Data Protection Regulation (EU) 2016/679 (GDPR) on data protection and privacy.

ATTACHMENT 1

DATA GATHERED FOR EACH PATIENT

- ◇ CENTER CODE
- ◇ UNIQUE PATIENT CODE
- ◇ ACCESS METHOD (TO BE COMPLETED ONLY THE FIRST TIME FOR EACH PATIENT)
- ◇ DATE (the CRF must be filled in each time the patient has a visit/admission)
- ◇ SENT BY:
 - FAMILY DOCTOR
 - OTHER SPECIALIST
 - ADVICE FROM A RELATIVE/ACQUAINTANCE
 - WEB SEARCH
- ◇ REFERRAL METHOD (TO BE COMPLETED ONLY THE FIRST TIME FOR EACH PATIENT)
 - ◇ FIRST ANESTHESIOLOGICAL VISIT
 - ◇ ANESTHESIOLOGICAL CHECK-UP EXAMINATION
 - UNDER CARE AT THE CENTER FOR:
 - > 5 years;
 - from 1 to 5 years;
 - from 1 year to 6 months; or 3 to 6 months;
 - < 3 months
 - ◇ ORDINARY HOSPITALIZATION
 - IN EMPLOYMENT AT THE CENTER FOR:
 - > 5 years;
 - from 1 to 5 years;
 - from 1 year to 6 months; or 3 to 6 months;
 - < 3 months
 - ◇ DAY HOSPITALITY (DAY SURGERY OR DAY HOSPITAL)
 - IN EMPLOYMENT AT THE CENTER FOR:
 - > 5 years;
 - da 1 a 5 anni;
 - da 1 anno a 6 mesi; o da 3 a 6 mesi;
 - < 3 mesi

LEVEL 1: DEMOGRAPHICS

- ◇ AGE
- ◇ SEX
 - M
 - F

STATE/COUNTY OF RESIDENCE

SCHOOL LEVEL

- ◇ Not Known
- ◇ Grade School
- ◇ High School
- ◇ University

WORK

- ◇ WORKER
- ◇ UNEMPLOYED

COMORBIDITIES

- ◇ CARDIOVASCULAR
- ◇ DIABETES
- ◇ RESPIRATORY
- ◇ AUTOIMMUNITY
- ◇ CHRONIC INFLAMMATION
- ◇ OTHER

LEVEL 2: DIAGNOSIS

TYPE OF PAIN

- ◇ PRIMARY CHRONIC
 - CHRONIC WIDESPREAD PAIN
 - FIBROMYALGIA
 - OTHER
 - CRPS

- HEADACHE OR OROFACIAL PAIN
- MUSCULOSKELATAL
 - LOW-BACK PAIN
 - ALTRO
- ◇ SECONDARY CHRONIC
 - ONCOLOGICAL
 - POSTSURGICAL
 - LUMBAR
 - CERVICAL
 - BREAST
 - INGUINAL HERNIA
 - THORACOTOMY
 - OTHER
 - POST TRAUMATIC
 - CRPS
 - OTHER
 - NEUROPATHIC
 - PERIFERAL
 - POST-TRAUMATIC
 - DIABETIC
 - TRIGEMINAL
 - POST-HERPETIC

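### Attachment 1, the stated list of data collected, has no field for adverse events, pain duration, number of specialists contacted, or whether a therapy ticked at entry is new or ongoing

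*Protocol*

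**What the plan says.** Section 5 of the Protocol (Data gathered) describes the registry's content in prose and then points to the attachment: "Specifically, the data collected is shown in Attachment 1". The same paragraph includes "the duration of the pain (> 5 years; from 1 to 5 years; from 1 year to 6 months; from 3 to 6 months") and "the number of other medical specialists contacted for the pathology being studied".

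Section 5 (Enrollment procedure) adds that, for patients enrolled at a check-up or during an admission, time in care at the center and "invasive procedures previously undertaken, the drugs prescribed, will be collected".

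Section 10 states: "Complications and adverse events that occur during follow-ups will be recorded in the registry".

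Two stated aims depend on timing:
- Secondary Outcome 4 (Section 2, Objectives) groups clinical variables by type of treatment and by "the timing of the start of treatment with respect to the onset of pain".
- Secondary Endpoint 4 (Section 6) names "the time between treatment and clinically significant improvement" among the variables to be described.

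Attachment 1 holds center and patient codes, visit date, referral source and method, demographics, comorbidities, type and area of pain, the BPI items, examinations, and tick lists of therapies.

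**The concern.** The text makes promises that the data list does not carry out. A later analysis plan can choose among recorded variables, but it cannot recover one that was never recorded. The consequences differ by item:

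- **Adverse events:** a commitment in Section 10 has no place in the record.
- **Pain duration:** without it the start of treatment cannot be placed relative to the onset of pain, so that grouping in Secondary Outcome 4 is lost.
- **Therapy status at entry:** a drug or implant already in use, or a block done earlier, looks the same as one begun that day. Time from treatment to improvement then has no clear origin. Section 8 also measures treatment effect as change relative to the baseline score, and for therapy already running that baseline is an on-treatment score.
- **Specialists contacted:** a promised descriptive variable is missing, though no stated endpoint uses it.

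**Working it through.** The protocol gives no figure to reproduce. The check compares each promise with the fields of Attachment 1.

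**Items listed in Section 5 (Data gathered).** There are 11: demographics, comorbidities, pain duration, type of pain, location, intensity, interference, treatments, tests, number of specialists contacted, referring professional. Nine have a field in Attachment 1. Pain duration and the specialist count do not: 11 − 9 = 2. Adverse events, from Section 10, are a third promised item without a field.

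| Promised or needed | Where | Nearest field in Attachment 1 | Does it serve? |
|---|---|---|---|
| Complications and adverse events | Section 10 | none | No |
| Pain duration, four bands | Section 5 | "UNDER CARE AT THE CENTER FOR" and its year bands | No: this is time in care, not time since onset, and it sits under three of the four referral methods, so first-visit patients have no time band |
| Number of other specialists contacted | Section 5 | referral source | No: a source, not a count |
| Earlier procedures and drugs, and start of treatment | Sections 2, 5, 6 | Level 3 tick lists | Not at entry: no status, no start date |

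**Therapies in Level 3.**
- Drugs: 3 (SNRI, gabapentinoids, tricyclics) + 13 opioids + 4 (NSAIDs, coxib, paracetamol, other) = 20.
- Infiltrative: 5. Neuromodulatory or neuroablative: 5. Implants: 5.
- Total: 20 + 5 + 5 + 5 = 35.
- With a start date or a new, ongoing or previous marker: 0 of 35.
- With an entry for number of days: 2 of 35 (NSAIDs and coxib), and that entry describes the regimen.

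**What the visit date does supply.** The form is dated and completed at each visit or admission. A therapy first ticked during follow-up therefore has a visit-based start, and an interval to improvement can be derived for it. The gap is limited to therapy recorded at the entry visit.

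**How many patients this could touch.** Section 8 expects 2500 patients. The protocol does not give the share enrolled at a check-up or admission, so three shares are assumed for illustration:
- 0.25 × 2500 = 625
- 0.50 × 2500 = 1250
- 0.75 × 2500 = 1875

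First-visit patients already treated elsewhere would add to these numbers.

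**The case against.** The strongest reply runs as follows. No passage promises a therapy-status marker in so many words. A figure at the end of the enrollment procedure is not visible in the text at hand and might show how retrospective data are entered. The referral-method field already separates first visits from patients in care. Phase 1 exists to structure the dataset, and the text of Section 5 itself specifies the pain-duration bands, so the working form may already include them. Adverse events and the specialist count feed no objective or endpoint, and treatment-to-improvement time is only one example in a descriptive list.

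Part of this stands:
- The marker is an inferred need, drawn from Sections 2, 5 and 6.
- The specialist count is peripheral, and the adverse event gap is a broken commitment rather than a lost endpoint.
- The absence of a time-in-care band for first visits is natural in itself; the defect is the missing pain-duration field.
- The assumed shares have no basis in the protocol. The count of therapies depends on a convention: splitting the two spinal cord stimulation entries by level gives 37 instead of 35, with the number marked still 0.

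The rest does not remove the point. Section 5 names Attachment 1, not the figure, as the list of data. The table of contents for Attachment 1 also shows no heading for adverse events, pain duration or previous therapy, so loss in text extraction is unlikely. Referral method identifies patients in care, but not which of their therapies were already running. Phase 1 makes correction cheap; it does not make the document consistent.

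**Conclusion.** The concern holds. Three promised items (adverse events, pain duration, number of specialists contacted) have no field in the list that the protocol says defines its data, and none of the 35 listed therapies can be marked as new or ongoing at entry. The most consequential gaps are pain duration and therapy status, because one component of Secondary Outcome 4 cannot be formed and one variable of Secondary Endpoint 4 is ambiguous for therapy present at enrollment. Timing for therapy begun during follow-up is not affected.

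The conclusion assumes that exactly the listed fields are collected; the working REDCap form may hold more. The patient numbers are illustrations on assumed shares, not estimates. This should be corrected before phase 2, but it does not undermine the registry as a whole.

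**What to change.** Before phase 2, reconcile Attachment 1 and the REDCap form with Sections 2, 5, 6 and 10:

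1. **Adverse events:** one item at each follow-up, with yes/no, type, date and related therapy.
2. **Pain duration at enrollment:** at least the four bands of Section 5, preferably an approximate month and year of onset.
3. **Therapy status at entry:** for each therapy ticked, one item (new today, ongoing, previous), with an approximate start date if ongoing. State that treatment-to-improvement time is calculated only for therapies started at or after enrollment.
4. **Specialists contacted:** a count. Since no endpoint uses it, withdrawing the promise from Section 5 would also restore consistency.

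A separate minor point: Section 4 sets an NRS entry criterion, while Attachment 1 records pain scores only as BPI-S items. State which item corresponds to it.

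The cost is three short items plus a status item that opens only for ticked therapies: 35 possible branches to build, few shown per patient. It should add only a few minutes of data entry, mainly at enrollment, and needs no extra visits or procedures. The drawback is that onset and earlier start dates will rest on recall or the chart. Phase 1, whose purpose is to structure the dataset, is the natural time to do it.

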11. ADMINISTRATIVE/REGULATORY CONSIDERATIONS

Economic considerations

No additional costs will be charged to the Healthcare System.

Insurance considerations

Given the observational nature of the study and which involves recording what happens in common clinical practice without deviations from the standard of care in each participating center, an additional insurance policy to that already provided for normal clinical practice is not necessary.

12. ETHICAL CONSIDERATIONS

This observational study is designed and will be conducted according to the current protocol, in accordance with EU Directive 2001/20/EC relating to the implementation of the principles of good clinical practice in the conduct of clinical trials on medicinal products for human use, in accordance with the principles published in Good Clinical Practice (GCP) guidelines and in accordance with the Declaration of Helsinki on Ethical Principles for Medical Research Involving Human Subjects, adopted by the General Assembly of the World Medical Association (1996),

The investigator guarantees that personal patient data will be protected and processed in accordance with the General Data Protection Regulation (EU) 2016/679 (GDPR) on data protection and privacy.

ATTACHMENT 1

DATA GATHERED FOR EACH PATIENT

- ◇ CENTER CODE
- ◇ UNIQUE PATIENT CODE
- ◇ ACCESS METHOD (TO BE COMPLETED ONLY THE FIRST TIME FOR EACH PATIENT)
- ◇ DATE (the CRF must be filled in each time the patient has a visit/admission)
- ◇ SENT BY:
 - FAMILY DOCTOR
 - OTHER SPECIALIST
 - ADVICE FROM A RELATIVE/ACQUAINTANCE
 - WEB SEARCH
- ◇ REFERRAL METHOD (TO BE COMPLETED ONLY THE FIRST TIME FOR EACH PATIENT)
 - ◇ FIRST ANESTHESIOLOGICAL VISIT
 - ◇ ANESTHESIOLOGICAL CHECK-UP EXAMINATION
 - UNDER CARE AT THE CENTER FOR:
 - > 5 years;
 - from 1 to 5 years;
 - from 1 year to 6 months; or 3 to 6 months;
 - < 3 months
 - ◇ ORDINARY HOSPITALIZATION
 - IN EMPLOYMENT AT THE CENTER FOR:
 - > 5 years;
 - from 1 to 5 years;
 - from 1 year to 6 months; or 3 to 6 months;
 - < 3 months
 - ◇ DAY HOSPITALITY (DAY SURGERY OR DAY HOSPITAL)
 - IN EMPLOYMENT AT THE CENTER FOR:
 - > 5 years;
 - da 1 a 5 anni;
 - da 1 anno a 6 mesi; o da 3 a 6 mesi;
 - < 3 mesi

LEVEL 1: DEMOGRAPHICS

- ◇ AGE
- ◇ SEX
 - M
 - F

STATE/COUNTY OF RESIDENCE

SCHOOL LEVEL

- ◇ Not Known
- ◇ Grade School
- ◇ High School
- ◇ University

WORK

- ◇ WORKER
- ◇ UNEMPLOYED

COMORBIDITIES

- ◇ CARDIOVASCULAR
- ◇ DIABETES
- ◇ RESPIRATORY
- ◇ AUTOIMMUNITY
- ◇ CHRONIC INFLAMMATION
- ◇ OTHER

LEVEL 2: DIAGNOSIS

TYPE OF PAIN

- ◇ PRIMARY CHRONIC
 - CHRONIC WIDESPREAD PAIN
 - FIBROMYALGIA
 - OTHER
 - CRPS

- HEADACHE OR OROFACIAL PAIN
- MUSCULOSKELATAL
 - LOW-BACK PAIN
 - ALTRO
- ◇ SECONDARY CHRONIC
 - ONCOLOGICAL
 - POSTSURGICAL
 - LUMBAR
 - CERVICAL
 - BREAST
 - INGUINAL HERNIA
 - THORACOTOMY
 - OTHER
 - POST TRAUMATIC
 - CRPS
 - OTHER
 - NEUROPATHIC
 - PERIFERAL
 - POST-TRAUMATIC
 - DIABETIC
 - TRIGEMINAL
 - POST-HERPETIC
 - OTHER
 - CENTRAL
 - POST-ISCHEMIC
 - SM
 - TRIGEMINAL
 - NEURODEGENERATIVE DISEASES
 - HEADACHE OR OROFACIAL PAIN
 - VISCERAL
 - SKELETAL MUSCLE
 - LOW-BACK-PAIN
 - OTHER

AREA OF PAIN

- ◇ LOWER BACK PAIN

- ◇ THORACIC
- ◇ UPPER LIMBS
- ◇ LOWER LIMBS
- ◇ HEAD/NECK
- ◇ PELVIS

PAIN INTENSITY AND INTERFERENCE

- ◇ BPI-S

WORST PAIN IN THE LAST 24 HOURS

• 1 • 2 • 3 • 4 • 5 • 6 • 7 • 8 • 9 • 10

LEAST PAIN IN THE LAST 24 HOURS

• 1 • 2 • 3 • 4 • 5 • 6 • 7 • 8 • 9 • 10

AVERAGE PAIN IN THE LAST 24 HOURS

• 1 • 2 • 3 • 4 • 5 • 6 • 7 • 8 • 9 • 10

CURRENT PAIN

• 1 • 2 • 3 • 4 • 5 • 6 • 7 • 8 • 9 • 10

HOW MUCH RELIEF HAVE YOU HAD FROM THE THERAPY (%)

• 10 • 20 • 30 • 40 • 50 • 60 • 70 • 80 • 90 • 100

BPI-I (PAIN INTERFERENCE ON)

ACTIVITY IN GENERAL

• 0 • 1 • 2 • 3 • 4 • 5 • 6 • 7 • 8 • 9 • 10

MOOD

• 1 • 2 • 3 • 4 • 5 • 6 • 7 • 8 • 9 • 10

ABILITY TO WALK

• 1 • 2 • 3 • 4 • 5 • 6 • 7 • 8 • 9 • 10

NORMAL WORKING ABILITY (both at home and outside)

• 1 • 2 • 3 • 4 • 5 • 6 • 7 • 8 • 9 • 10

RELATIONSHIPS WITH OTHER PEOPLE

• 1 • 2 • 3 • 4 • 5 • 6 • 7 • 8 • 9 • 10

SLEEP

• 1 • 2 • 3 • 4 • 5 • 6 • 7 • 8 • 9 • 10

PLEASURE OF LIVING

• 1 • 2 • 3 • 4 • 5 • 6 • 7 • 8 • 9 • 10 • 1 • 2 • 3 • 4 • 5 • 6 • 7 • 8 • 9 • 10

REQUESTED EXAMS

- ◇ INSTRUMENTAL EXAMS
 - XRAY
 - MRI
 - SCINTIGRAPHY
 - EMG/ENG
 - OTHER
- ◇ LABORATORY EXAMS

COMPLETED EXAMS

- CLINICAL EXAMINATION OF SENSITIVITY
- QST-TEST
- DIAGNOSTIC BLOCK

LEVEL 3: THERAPY

PHARMACOLOGICAL THERAPY

- ◇ SNRI
- ◇ GABAPENTINOIDS
- ◇ TRICICLICS
- ◇ OPIOIDS
 - TRAMADOL
 - CODEINE/PARACETAMOL
 - OXYCODONE/PARACETAMOL
 - MORPHINE SR
 - MORPHINE IR
 - OXYCODONE
 - OXYCODONE/NALOXONE
 - HYDROMORPHONE
 - TAPENTADOL
 - TRANSDERMAL FENTANYL
 - TRANSMUCOSAL FENTANYL
 - BUPRENORPHINE
 - METHADONE

- ◇ NSAIDs
 - AS NEEDED
 - INTERVALS/REGULARLY (indicate how many days)
- ◇ COXIB
 - AS NEEDED
 - INTERVALS/REGULARLY (indicate how many days)
- ◇ PARACETAMOL
- ◇ OTHER

INFILTRATIVE THERAPY

- ◇ EPIDURAL
- ◇ INTRA-ARTICULAR (SHOULDER, KNEE, ANKLE, HIP, ECC)
- ◇ SPINAL FACET JOINTS
- ◇ SACRO-ILIAC
- ◇ PERIPHERAL NERVE

NEUROMODULATORY/NEUROABLATIVE THERAPY

- ◇ GANGLIAR RADIOFREQUENCY
- ◇ RADIOFREQUENCY OF PERIPHERAL NERVES
- ◇ CRIOAMODULATION
- ◇ EPIDUROLYSIS
- ◇ EPIDUROSCOPY

IMPLANTS

- ◇ SCS NON-RECHARGABLE
 - CERVICAL
 - DORSAL
- ◇ SCS RECHARGABLE
 - CERVICAL
 - DORSAL
- ◇ STIMULATION OF PERIPHERAL NERVE
- ◇ GANGLIAR STIMULATION
- ◇ INTRATHECAL PUMP

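### On the fields listed in Attachment 1, contacts after enrolment cannot be split into visits and hospitalizations, although secondary endpoint 3 counts the two separately

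*Protocol*

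**What the plan says.** Section 6, Secondary Endpoint, item 3 defines resource use by two separate counts. The first is "Resources used: Number of visits to the center for each patient in a year"; the second is "Number of ordinary or day hospitalizations for each patient in a year".

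Section 5 (Data gathered) points to the attachment for the detail: "Specifically, the data collected is shown in Attachment 1".

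Attachment 1 has two headings that could hold the type of contact:

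- "REFERRAL METHOD (TO BE COMPLETED ONLY THE FIRST TIME FOR EACH PATIENT", under which the options first visit, check-up, ordinary hospitalization and day hospital are listed;
- "ACCESS METHOD (TO BE COMPLETED ONLY THE FIRST TIME FOR EACH PATIENT", which has the same once-only instruction and no options of its own.

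The item that recurs is the date: "DATE (the CRF must be filled in each time the patient has a visit/admission". A visit and an admission both trigger the same form.

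For later contacts, Section 5 (Follow-up procedure) says it will be possible to "fill in the data relating to the intensity of pain and the treatments undertaken", and to change or add an etiological diagnosis. It does not mention the type of contact.

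**The concern.** An endpoint that counts admissions separately from visits needs every contact to be labelled as one or the other. The attachment collects that label once per patient, at entry, and tells sites not to repeat it. A site that follows the form exactly would enter a later day-hospital admission and a later outpatient check-up as two dated forms with nothing to tell them apart by setting.

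At stake is one item of a descriptive secondary endpoint, but it is the only endpoint in Section 6 that counts hospitalizations. Section 1 gives health planning as one purpose of the database. No analysis plan can recover a label that was not collected. Because the key that identifies patients stays at the local sites (Section 5), a later repair would mean going back to charts centre by centre.

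**Working it through.** The protocol gives no figure to reproduce here. The check is whether each quantity in the endpoint can be derived from the listed fields.

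**Inputs**

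| Needed or collected | Where | How often |
|---|---|---|
| Visits per patient per year | Section 6, secondary item 3 | endpoint |
| Ordinary or day hospitalizations per patient per year | Section 6, secondary item 3 | endpoint |
| Contact type (four options) | Attachment 1, referral method | once per patient |
| Access method (no options shown) | Attachment 1 | once per patient |
| Date of visit or admission | Attachment 1 | every contact |
| Pain intensity, treatments, revised diagnosis | Section 5, Follow-up procedure | follow-up contacts |
| Procedures and implants, without setting | Attachment 1, Level 3 | treatment fields |

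**Derivation.** Let n be the number of dated forms for a patient, assuming one form per visit or admission as the attachment instructs. Let a = 1 if the enrolment contact was an admission and a = 0 otherwise.

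1. Total contacts = n. Derivable.
2. Type of the enrolment contact = a. Derivable from the once-only block.
3. Hospitalizations = a + (unknown number among the n − 1 later contacts). The listed fields place this only between a and a + (n − 1).
4. Visits = n − hospitalizations. The range has the same width, n − 1.

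As an illustration only, take a patient who enters at a first visit and later has one ordinary and two day admissions. Then n = 1 + 1 + 2 = 4 and a = 0. The listed data are compatible with anything from 0 to 3 hospitalizations, and with 4 down to 1 visits.

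**Could another field stand in?** The Level 3 treatment list names epidurals, radiofrequency, implants and similar procedures, but gives no setting. A tick there does not separate outpatient care, day hospital and ordinary admission.

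**Does the layout matter?** If the four options really belong to the access-method heading, the result is the same, since that heading is also once-only.

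**Side point: the yearly window.** Both counts are per year, so it matters how many patients can be observed for 12 months. Under uniform accrual, the share with less than 12 months depends on which statement applies:

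- Section 3 dates: enrolment 01/06/2023 to 01/03/2025 (21 months), follow-up to 01/09/2025. Patients enrolled in the last 6 months fall short: 6/21 = 29%.
- Follow-up only until enrolment ends (wording in Sections 3 and 5), on the same enrolment dates: 12/21 = 57%.
- Section 5: 12 months of enrolment, database open 3 months after the last patient. Those enrolled after month 3 fall short: 9/12 = 75%.

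The main point does not depend on these figures.

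**The case against.** The strongest objection is that Attachment 1 is not the whole electronic form. Pain duration and the number of other specialists consulted (Section 5), and complications and adverse events at follow-up (Section 10), are all said to be recorded, yet none is listed there. A figure at the end of the enrolment procedure in Section 5 is not shown in the text at hand. A repeated contact-type field could therefore exist in the database. This stands as a limit: the claim is about the listed fields. It does not remove the conflict, because the attachment does more than stay silent. It expressly restricts the field to the first time.

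A second objection is that the block looks like a labelling slip. The referral-method heading carries visit types, while the referral source sits under a different item, so the once-only instruction may have been meant for referral source and time in care. That is plausible, and it would make the correction easier, but a site can only follow the form as written.

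A third objection concerns importance. Hospitalizations are half of one descriptive secondary item, and the matching objective in Section 2 speaks of visits and time and does not mention admissions. The primary endpoint's number of accesses stays countable. Phase 1 is there to settle the dataset and the data entry methods. All of this stands and lowers the severity.

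Two stronger readings are tempting. A reader might infer that patients with later admissions would be counted as having none. The documents do not support that: an uncollected type is missing, and nothing in the protocol tells the analyst to code it as zero. A reader might also infer that a fixed share, such as 29%, cannot supply a yearly count. That figure is one of three the protocol allows, and adjusting counts for unequal follow-up is ordinary analysis-plan content.

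**Conclusion.** The point holds in a limited form. Secondary endpoint 3 and Attachment 1 do not fit together: on the listed fields, at most one admission per patient can be identified, the one at enrolment, and the type of all n − 1 later contacts is missing. Neither of the two counts can be formed separately; their total can.

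This rests on two assumptions: that sites follow the once-only instruction, and that no unlisted field repeats the contact type. The severity is should-fix. The total number of accesses is unaffected, and the pain and interference outcomes do not depend on this field. The share of patients with under 12 months of follow-up, 29% to 75% under uniform accrual, is a side point and does not carry the conclusion.

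**What to change.** In Attachment 1, make the type of contact (first visit, check-up, ordinary hospitalization, day hospital) a required item on every dated form. Keep the once-only instruction for the referral source and for the band recording how long the patient has been in the centre's care. In Section 6, secondary item 3, state that both counts are derived from the repeated item. If the electronic form already repeats it, correct the attachment to say so.

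The cost is one extra tick per contact, one existing field set to repeat, and one sentence in Section 6. No additional procedure is needed. The change is cheapest if made in Phase 1, before Phase 2 data accrue.
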